4.2.4 Global/Country Situation Summaries

The Coronavirus Disease of 2019 (COVID-19) pandemic was declared by the World Health Organisation on 11th March 2020 and is considered a global/country situation. The Ukraine/Russia crisis started on 24th February 2022 and is considered a global/country situation. Global/country situation summaries will be presented (see Section 4.5.1).

4.2.5 Japan-Specific Analysis

A subset of the planned outputs will be repeated for participants from Japan, as required for interactions with the Japanese Regulatory Agency. The outputs will be identified in the TLF mock shells.

4.3 Software

All report outputs will be produced using SAS[®] version 9.4 or a later version in a secure and validated environment.

4.4 Handling of Dropouts or Missing Data

Summary statistics will be based on non-missing values. Information on how missing data will be handled for UACR is provided in Section 4.10.2. Missing safety data will generally not be imputed. However, safety assessment values (vital signs, laboratory assessments excluding urine albumin, urine creatinine and UACR) of the form “<x” (i.e. below the lower limit of quantification [LLOQ]) or “>x” (i.e. above the upper limit of quantification) will be imputed as “x” in the calculation of summary statistics but displayed as “<x” or “>x” in the listings. Measurements of urine creatinine, urine albumin and UACR which are displayed as “<x” will be imputed by using half of the “x” value, as this represents the LLOQ, justified by assuming that any value is equally likely between 0 and the LLOQ. These imputations are required in order to effectively calculate the geometric mean.

Partial or missing dates

If the start date of the concomitant medication or AE is missing, the following rules will be applied:

- If the year is missing, the year should be imputed as the year that participant received the first dose of study treatment.
- If the year is available and the month and day are missing, then impute the month as January and the day as 01.
- If the year and month are available and the day is missing, impute the day as 01 (the first day of the month).
- If any of the above puts the date before the date of first dose of study treatment, a conservative approach is followed, and the date is imputed using the date of first dose if the year matches the year of the date of first dose of study treatment when only the year is available or if the year and month matches the year and month of the date of first dose of study treatment when only the year and month are available.

If the stop date of the concomitant medication or AE is missing and there is an indication that there should be a stop date (ongoing flag marked as “N” for concomitant medication, outcome reported as resolved/fatal for AE), the following rules will be applied:

- If the year is missing, the year should be imputed as the year that participant received the last dose of study treatment.

- If the year is available and the month and day are missing, then impute the month as December and the day as 31.
- If the year and month are available and the day is missing, impute the day as the last day of the month (e.g. 28, 29, 30 or 31).
- If any of the above puts the date after the date of end of study or date of death, the date is imputed using the earliest of the date of end of study and the date of death.

It is not expected to have missing dates for unscheduled laboratory or ECG data. However, if there are missing dates, for any derivations, the dates should be imputed following the rules for concomitant medications and AEs.

4.5 Study Subjects

4.5.1 Disposition of Subjects

A clear accounting of the disposition of all participants who enter the study (signed the informed consent form) will be provided, from screening to study completion.

The following summaries will be provided:

- A summary of the number of participants screened, screen failures, randomised, treated, completed treatment (a participant who has not prematurely discontinued IP during the study), completed treatment period (a participant who has completed the last visit during the treatment period i.e. Visit 7, or a later visit) and completed study (a participant who has completed the follow-up visit at Week 14), by treatment arm and overall. In addition, reasons for not being treated, not completing the treatment period and not completing the study will be summarised by treatment arm and overall (Analysis set: Screened).
- A summary of subject disposition related to the global/country situation (Analysis set: Full Analysis Set).
- A summary of the number of participants randomised per region, country and centre, by treatment arm and overall (Analysis set: All randomised set).
- A summary of Interactive Response Technology (IRT) stratification factors i.e. diabetes (DKD participants versus non-DM CKD participants) and baseline eGFR (≤ 45 mL/min/1.73 m² versus > 45 mL/min/1.73 m²) at randomisation by treatment arm and overall (Analysis set: All randomised set).
- A summary of global/country situation study disruptions (Analysis set: Full Analysis Set).

By-participant listings of disposition details for discontinued participants, participants completing the study, participants affected by the global/country situation and participants with reported issues in the Clinical Trials Management System due to global/country situation will be provided. In addition, a by-participant listing of the randomisation scheme and codes will be provided.

4.5.2 Protocol Deviations

According to ICH E3 guidelines version dated 1995 (ICH 1995),

“Protocol deviations consist of any change, divergence or departure from the study design or procedures defined in the protocol. Important protocol deviations (IPDs) are a subset of protocol deviations that may significantly affect the completeness, accuracy, and/or reliability of the study data or that may significantly affect a patient’s rights, safety or well-being.”

The impact of important protocol deviations on the efficacy results will be investigated by assessing the robustness of the study results and conclusions to the choice of analysis set, both including and excluding data potentially affected by important protocol deviations.

Important protocol deviations and any action to be taken regarding the exclusion of participants or affected data from specific analyses are defined in the project-specific Protocol Deviation Specification.

For this study, the following general categories will be considered IPDs and will be summarised in the CSR:

- Deviation 1: Participants who did not meet the inclusion criteria or met exclusion criteria and received study treatment.
- Deviation 2: Participants assigned to treatment who received their assigned study treatment at an incorrect dose at one or more occasions or who received a study treatment to which they were not assigned.
- Deviation 3: Participants who received prohibited medications during study treatment period or as specified in Section 6.5.1 in the CSP.
- Deviation 4: Participants who met study treatment discontinuation criteria but continued study treatment.
- Deviation 5: Participants who persistently missed procedures related to key efficacy and safety objectives.
- Deviation 6: Missed visits, assessments, or treatments that, in the Investigator's opinion, were due to the COVID-19 pandemic and there was a significant effect on EITHER completeness, accuracy, and/or reliability of the participant's data, OR the participant's rights, safety or well-being.

In addition to classifying protocol deviations (PDs) as important or non-important, PDs are also evaluated for whether they can be classified as resulting from COVID-19 or the Ukraine/Russia crisis.

The number and percentage of participants with any IPD will be summarised for each IPD category based on the full analysis set (FAS). There will be additional sections of the summary for IPDs related to COVID-19 and the Ukraine/Russia crisis. Participants with more than one deviation in the same IPD category will be counted once for that IPD category. Any participants who have deviations in more than one IPD category will be counted once in the overall summary.

A list of all PDs, including those reported by monitors, will be reviewed and decisions regarding how to handle these deviations will be documented by the study team physician, clinical pharmacology scientist and statistician prior to database lock (DBL). The final classification will be made prior to database lock.

Programmable PDs will be detected from the data recorded in the clinical database and will be reviewed at regular PD review meetings. At this meeting, the programmatically derived PDs will be checked to ensure that they have been correctly classified as important or not important PDs.

On an ongoing basis throughout the study, monitoring notes or summaries will also be reviewed to determine any important post entry deviations that are not identifiable via programming.

The final classification of IPDs will be made prior to DBL or data cut-off for final analysis. Any other deviations from monitoring notes or reports will be reported in an appendix to the CSR.

A by-participant listing of important protocol deviations will be provided.

4.6 Analysis Sets

The following summaries will be provided:

- A summary of the number of participants in each analysis set by treatment arm and overall. Exclusions from each analysis set will also be summarised by reason.

By-participant listings of participants excluded from each analysis set and the reasons for exclusion from each analysis set will be provided.

Table 6 Analysis Sets

Population/ Analysis set	Data selection as indicated in Table 4	Description
Screened	D+M	All participants who signed the informed consent form.
Descriptive Analysis Set	D	All participants randomised and who are to be presented only descriptively as indicated with D in Table 4. Participants are evaluated according to the treatment assigned at randomisation.
All Randomised Set	M	All participants who are randomised. Participants are evaluated according to the treatment assigned at randomisation.
Full Analysis Set (FAS)	M	All participants who are randomised and receive any study treatment. Participants are evaluated according to the treatment assigned at randomisation.
Per Protocol Analysis Set (PPS)	M	A subset of the FAS consisting of all participants who completed at least 6 weeks of treatment and do not have any protocol deviations classified as important. All decisions to exclude participants from the PPS will be made and documented prior to the unblinding of the study.
Safety Analysis Set	M	All participants who are randomised and receive any study treatment. Participants are evaluated according to the actual treatment they received. If a participant received a different treatment dose than randomised throughout the study, they will be analysed according to the treated dose, not the randomisation dose. If a participant received investigational product from the wrong kit for only part of the treatment duration but they received the correct kit at some point during treatment duration, they will be analysed according to their planned randomisation arm. If a participant receives multiple incorrect kits and never receives the correct kit during treatment duration, they will be analysed according to their first treated dose. The Safety Analysis Set will be used for all safety analyses, unless otherwise specified.
Ambulatory Blood Pressure Monitoring Set	D	All participants in the Descriptive Analysis Set who have valid ambulatory BP data for change from baseline analyses.

Population/ Analysis set	Data selection as indicated in Table 4	Description
Pharmacokinetic Analysis Set	M	
All participants in the FAS who have at least one detectable zibotentan or dapagliflozin plasma concentration measurement post-treatment. Participants are evaluated according to the actual treatment they received.
 
If a participant received a different treatment dose than randomised throughout the study, they will be analysed according to the treated dose, not the randomisation dose. If a participant received investigational product from the wrong kit for only part of the treatment duration but they received the correct kit at some point during treatment duration, they will be analysed according to their planned randomisation arm. If a participant receives multiple incorrect kits and never receives the correct kit during treatment duration, they will be analysed according to their first treated dose.
 
The Pharmacokinetic Analysis Set will be used for all PK analyses.

Participants or sites identified prior to database lock with major Good Clinical Practice violations and where the integrity of the data is strongly questioned through thorough independent investigations will be excluded from all analyses and all analysis sets.

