9.3 Populations for Analyses

The following populations are defined:

Table 6 Populations for Analysis

Population/Analysis set	Description
Screened	All participants who signed the ICF.
Full Analysis Set (FAS)	All participants who are randomised and receive any study intervention. Participants are evaluated according to the treatment assigned at randomisation. The FAS will be used for all analyses of demographic baseline characteristics and efficacy data.
Per Protocol Analysis Set (PPS)	A subset of the FAS consisting of all participants who completed at least 6 weeks of treatment and do not violate the terms of the protocol in a way that may affect the primary efficacy endpoint significantly. All decisions to exclude participants from the per protocol analysis set will be made and documented prior to the unblinding of the study.
Safety Analysis Set (SAS)	All participants who are randomised and receive any study intervention. Participants are evaluated according to the actual treatment they received. If a participant received a different treatment dose than randomised throughout the study, they will be analysed according the treated dose, not the randomisation dose. If a participant received investigational product from the wrong kit for only part of the treatment duration, they will be analysed according to their randomisation dose. The SAS will be used for all safety analyses.
Ambulatory Blood Pressure Monitoring population	All participants in the FAS who have valid ambulatory BP data for change from baseline analyses.
Pharmacokinetic Analysis Set	All participants in the FAS who have at least one detectable zibotentan or dapagliflozin plasma concentration measurement post-treatment. The Pharmacokinetic Analysis Set will be used for all PK analyses.

Additional analysis sets may be defined in the Statistical Analysis Plan (SAP) for exploratory analyses. Participants or sites identified prior to database lock with major GCP violations and where the integrity of the data is strongly questioned through thorough independent investigations will be excluded from all analyses and all analysis sets.

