4.11 Safety Evaluation

All safety summaries and analyses will be based upon the Safety Analysis Set as defined in Section 4.6 and the on-treatment period as defined in Section 4.2.1, unless otherwise specified. Safety summaries will be presented by treatment arm.

Change from baseline will be calculated as the difference between the post-dose value at each time point and the last non-missing value prior to or on the same date as administration of the first dose of investigational products.

Individual safety and tolerability data will be provided in data listings and summarised as appropriate by treatment and overall. Continuous variables (laboratory parameters, ECG, and vital signs) will be summarised using descriptive statistics (n, mean, SD, minimum, median, and maximum) as appropriate by scheduled assessment time point. Where applicable, data will be summarised for the observed value, and for the corresponding change from baseline/screening. Categorical variables will be summarised in frequency tables (counts and percentage) as appropriate by scheduled assessment time point.

Changes from baseline in categorical data will be summarised using shift tables where appropriate.

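### The exclusion for major GCP violations with seriously doubtful data reaches every analysis set, so dosed participants' safety events have no assured place in the report

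*SAP*

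**What the plan says.** The rule has two conditions and a time limit. SAP 4.6 concerns participants or sites found, before database lock, to have major GCP violations; of these, those "where the integrity of the data is strongly questioned through thorough independent investigations will be excluded from all analyses and all analysis sets". Protocol 9.3 has the same trigger, and its consequence is that such participants or sites "will be excluded from all analyses and all analysis sets". Neither document exempts safety or disposition.

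The sets it cuts across are defined in SAP 4.6, Table 6. Screened is everyone who signed consent, and All Randomised is everyone randomised. The Safety Analysis Set is "All participants who are randomised and receive any study treatment. Participants are evaluated according to the actual treatment they received". SAP 4.11 then states: "All safety summaries and analyses will be based upon the Safety Analysis Set as defined in Section 4.6", unless otherwise specified. SAP 4.11.5.1 counts fluid-related events of special interest on that set, by arm.

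On participant flow, SAP 4.5.1 promises: "A clear accounting of the disposition of all participants who enter the study (signed the informed consent form) will be provided". The main disposition table is to be built on the Screened set.

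SAP 4.6 also plans a count of exclusions from each set by reason, and a by-participant listing of who was excluded and why. Protocol 8.3.7 requires every SAE to be entered in the eCRF and reported to the sponsor.

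**The concern.** Leaving a site whose measurements cannot be trusted out of the UACR estimate is defensible. Taking its participants out of every set is a different step, because people who were given study drug were exposed to it whatever the quality of their UACR data. Under the literal rule, a death, a heart failure hospitalisation or a fluid event in such a person would appear in no planned safety table, although the Safety Analysis Set is defined as everyone randomised and dosed.

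This matters because fluid retention and heart failure are the named zibotentan risks in protocol Table 2, and SAP 4.10.2.7 foresees modelling of safety events to help select the dose for future studies. A reader of the report would also meet a disposition table that does not match its own definition. For the primary endpoint, there would be no result showing whether the conclusion depends on the exclusion.

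**Working it through.** **The plan's own figure.** SAP 4.14 gives 415 main-analysis participants: 166 + 166 + 83 = 415. Inflating the evaluable numbers for 10% drop-out gives 150/0.90 = 166.7 and 75/0.90 = 83.3, in line with 166 and 83. No figure in either document describes how many participants the rule might remove, so the main check is a comparison of texts.

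**Rule against definitions.**

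| Item | Own definition or use | Under the literal rule |
|---|---|---|
| Screened (SAP Table 6) | everyone who signed consent | excluded participants missing |
| Disposition (SAP 4.5.1) | everyone who signed consent, on Screened | excluded participants missing |
| All Randomised (SAP Table 6) | everyone randomised | excluded participants missing |
| Safety (SAP Table 6, 4.11, 4.11.5.1) | everyone randomised and dosed | excluded dosed participants and their events missing |

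**Where the safety events could still appear.** Protocol 9.4.3.1 plans one AE listing for the safety set and one for participants never exposed to study drug. An excluded but dosed participant belongs to neither. The exclusion listing in SAP 4.6 gives the person and the reason, not the events.

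**Whether a with-them efficacy result is available.** The sensitivity analyses in SAP 4.10.2.2 use the PPS or imputation on the FAS. The treatment-policy analysis in SAP 4.10.2.6 uses the All Randomised Set. The rule empties all of these of the excluded participants.

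**Scale, for illustration.** About 220 sites are planned (SAP 3.1).

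- Average main-analysis participants per site: 415/220 = 1.9, or 1.9/415 = 0.45% of the total.
- A site with 10 such participants (assumed): 10/415 = 2.4%, leaving 405.

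**Direction, for illustration.** The SAP compares fluid events with dapagliflozin by relative risk. Assume 20/166 events on zibotentan 1.5 mg and 12/166 on dapagliflozin, so RR = (20/166)/(12/166) = 1.67. These event counts are assumptions, not trial data.

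| Removed per arm | Events removed (zibotentan, dapagliflozin) | RR |
|---|---|---|
| 2 | 1, 0 | (19/164)/(12/164) = 1.58 |
| 5 | 2, 0 | (18/161)/(12/161) = 1.50 |
| 10 | 4, 1 | (16/156)/(11/156) = 1.45 |
| 5 | 0, 1 | (20/161)/(11/161) = 1.82 |

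The relative risk can fall or rise, and does not change if nobody is excluded.

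**The case against.** The strongest reply is that this is a narrow safeguard against untrustworthy data, with its consequences already made visible. Much of that stands, and it rules out several stronger readings that a reader might infer:

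- *Any major GCP violation removes a participant.* Not so. Data integrity must also be strongly in doubt after independent investigation, and the case must be identified before database lock.
- *Participants vanish silently and the flow cannot be reconciled.* Not supported. The exclusion summary and listing in SAP 4.6 let a reader count, identify and explain them. What remains is that the Screened-based table contradicts its own definition.
- *Serious events are lost.* Not supported. SAEs remain in the eCRF and in reporting to the sponsor (protocol 8.3.7). SAP 4.11.2 also says that all AEs will be listed, and it is unclear whether the exclusion reaches listings. But protocol 9.4.3.1 ties the AE listings to the safety set and to unexposed participants, so inclusion is not assured.
- *Harm is understated.* Counts and exposure would be lower, but events and person-time leave together, so rates and relative risks have no fixed direction.
- *The exclusion could be decided with knowledge of treatment.* Protocol 6.3 largely covers this: codes stay unbroken for the planned analyses until evaluability decisions are documented, and unblinded roles stay out of blinded data decisions.

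It can also be said that doubtful sites may have unreliable dosing and event records. Adding participants from a site that under-reported events would dilute harm rates. That is a fair argument against simply returning them to the main safety tables. It is not an argument against showing their events separately.

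SAP 4.5.2 promises to test robustness with and without data affected by important deviations. It concerns efficacy and works through the choice of analysis set. Participants who are in no set cannot be restored that way.

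**Conclusion.** The point holds as a defect in a pre-specified rule. The blanket exclusion and the Screened, All Randomised and Safety definitions cannot all be applied as written. If the rule were triggered, two things would be missing: an assured presentation of safety events in dosed excluded participants, and an efficacy result that includes them.

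The conclusion rests on a literal reading of the scope wording, which is the same in both documents. It does not rest on any known exclusion, since neither document says that a participant or site met the rule. The size is therefore unknown. On the average site size it would be small, and larger only if a high-recruiting site or several sites were affected. The change is worth making because it is cheap and is best settled before anyone knows whom it affects.

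**What to change.** Reword SAP 4.6 and protocol 9.3 as follows:

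1. Limit the exclusion to the efficacy analyses on the FAS and PPS.
2. Keep affected participants, flagged, in the Screened, All Randomised and disposition counts.
3. Present the deaths, SAEs, discontinuations and fluid-related events of dosed excluded participants in a separate listing, or give the safety tables with and without them.
4. Run the primary model once with these participants included, as a named sensitivity analysis.

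Because the treatment-policy analysis in SAP 4.10.2.6 uses the All Randomised Set, the new wording should also say whether flagged participants count there. If the protocol text is not amended, SAP 4.15 is the place to record the departure.

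The cost is the rewording, one flag variable, one listing or a repeat of selected safety tables, and one further model run. The downside is that some doubtful records will appear in the report, marked as such.
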